#### 1.4.2 Analytic framework

A review of factorial randomized control trials identified that the appropriate analytics model, in general, would adhere to Equation 1 (see below), assuming that the basic functional form for regression is the appropriate approach. This approach was used per Montgomery et al. Variations to this functional form are noted below.

$$\text{Eq. 1: } y = X_{Tech} + X_{Touch} + X_{Tech*Touch}$$

To address potential differences in variance associated with the multi-site and pragmatic aspects of the study (e.g., expansion of the study after it was originally conceptualized and operationalized, differences in policies and procedures across hospitals and units), we performed cluster-robust standard errors in the estimation of the outcomes. The analysis clusters study participants by the hospital where the study participant was enrolled. To validate this assumption, a sensitivity analysis was performed on patients transferred to different hospitals within the medical center.

Further, to account for heterogeneity in duration of patient access to the inpatient portal, we included the length of tablet provisioning, measured in days, as an offset parameter in all models.

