2.2 Objectives

The ***High Tech and High Touch (HT2): Transforming patient engagement throughout the continuum of care by engaging patients with portal technology at the bedside*** study at OSU Wexner Medical Center (OSUWMC) sought to study how the deployment of a commercial (i.e., Epic Systems) inpatient portal, MyChart Bedside, impacted identified patient outcomes. To evaluate the impact of function set and training

on inpatient (i.e., MyChart Bedside) and outpatient (i.e., MyChart) portal use, the HT2 Study²⁰ was designed as a large-scale, pragmatic randomized controlled trial across six hospitals in a healthcare system.

Using a two-by-two factorial design, HT2 simultaneously examined the effects of two approaches to portal training with two versions of the inpatient portal. HT2 was designed to test four study hypotheses:

Hypotheses related to primary outcomes:

H1: Patients assigned to the High intervention levels for Tech and Touch will demonstrate higher use of MyChart Bedside.

H2: Patients assigned to the High intervention levels for Tech and Touch will demonstrate higher levels of satisfaction with (H2a) and involvement in (H2b) their care experience.

Hypotheses related to secondary outcomes:

H3: Patients assigned to the High intervention levels for Tech and Touch will demonstrate higher rates of outpatient portal adoption (i.e., of Epic's MyChart) for those admitted without prior outpatient portal use (H3a), and higher use of MyChart for those admitted who had previously used the outpatient portal (H3b).

H4: Patients assigned to the High intervention levels for Tech and Touch will demonstrate higher levels of self-efficacy.

To prevent outcome reporting bias and data-driven analysis of results, we produced this detailed statistical analysis plan. The plan was originally developed and drafted prior to examination of the data, and in the absence of randomization knowledge. The plan has been revised as the analysis has proceeded.

Section 3: Study methods

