3.2.1 Tech randomization

Tech randomization was accomplished using a 4-digit random number table generated using Stata version 14.0 which was used as a comparison table against the last four digits of the patient's Medical Record Number (MRN) which was assigned prior to study assignment. A preliminary simulation analysis found that random assignment using this model created appropriately sized groups of 40% and 60%.

Individuals who had access to the Full version of MyChart Bedside prior to enrollment in the study (i.e., those patients who were admitted to the Cancer Center, which was not included as a site, or patients who had used MyChart Bedside during the pilot phase of implementation in which only Full-Tech was available) maintained their Full-Tech status and were excluded from randomization if they were transferred to a unit included in the study.

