3.2.2 Touch randomization

The study protocol included a series of robust approaches to randomization. Generally, Touch randomization occurred at consent using the randomizer function in Qualtrics which was used for both consent and survey data collection. The Protocol included a procedure for the assignment of Touch in cases where the patient was checked in after daily census and was not included in the Qualtrics randomization (i.e., due to timing of reconciliation between report pulls and the start of the work day). In those cases, a predefined randomization table was used to assign Touch status.

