4.2.1 Operational protocol amendments

Operational protocol amendment 1: Improve enrollment yield (Jan 2017)

A research team member could visit the patient to remind them to complete the survey, limited to three visits per patient, once per day. Patients without completed surveys could also be visited on subsequent hospital admissions to complete their survey.

Operational protocol amendment 2: Improve data quality (Jul 2017)

A confirmation was added to each page of the survey to inform respondents when they had left questions unanswered on a page. They could continue to advance if that was their preference.

Operational protocol amendment 3: Intervention available after consent (Feb 2018)

TNs were allowed to make first contact for the High-Touch intervention once the patient consented—no longer waiting for a complete Admission survey. The TN should work with the patient to walk them through completing the survey during the intervention.

Operational protocol amendment 4: Intervention assignment (Mar 2018)

Individuals that had activated a MyChart Bedside account or were in a Full-Tech unit prior to the study start were manually assigned Full-Tech regardless of their MRN.

Individuals who were found to have accessed both Full and Lite versions over the course of the study were to be excluded from the analysis for this study.

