## Section 1: Statistical analysis

### 1.1 Confidence intervals and p-values

For all statistical tests, a p-value of 0.05 was used to assess significance and 95% confidence intervals were reported. No adjustment was done for multiple hypothesis testing.

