#### 1.5.1 Outcome 1 – Number of MyChart Bedside sessions within the enrollment admission was dependent on treatment

*Dependent variable specification:* The count of MyChart Bedside sessions for the admission associated with study enrollment.

- Enrollment admission was defined as the admission when the patient was enrolled in the study.

*Statistical model:* Negative binomial model with non-interacted and interacted study arms as binomial predictors.

---

ii Preliminary analysis of adoption rates for the outpatient portal revealed a rapid decrease in the numbers following the first few months, which motivated us to set the value for the cutoff date at 90 days in order to more conservatively attribute portal use to an individual's participation in the study.

*Covariates:* No covariates were added to this analysis.

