### 1.5.2 Outcome 2 – Comprehensive use was dependent on treatment

*Dependent variable specification:* A binary variable identifying participants that used all available functions based on their Tech arm assignment (1 = comprehensive functions user; 0 = not a comprehensive functions user).

- The definition of “comprehensiveness” was tested in two different ways:
  - **Definition 1: Based on use of all available functions:** Users were considered comprehensive functions users when they reached a threshold number of functions used based on their Tech Arm. For Lite-Tech users, this threshold was three selectable functions available—Bedside Tutorial, Dining on Demand, and To Learn. For Full-Tech users, this threshold was eight of the 10 functions available, including the three functions available to Lite-Tech users.
  - **Definition 2: Based on use of the functions available to all users:** Users were considered comprehensive functions users when they used the three functions that were available to all users.

*Statistical model:* Logistic regression model with non-interacted and interacted study arms as binomial predictors.

*Covariates:* No covariates were added to this analysis.

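### Standard errors are clustered on at most six hospitals with no small-cluster method: with a normal reference, the 5% tests for H1 to H3 run at about 11% if hospitals are equal in size, and higher if not

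*SAP*

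**What the plan says.** SAP 1.4.2 estimates all outcomes with cluster-robust standard errors, to allow for differences in policy and practice across hospitals and units: "The analysis clusters study participants by the hospital where the study participant was enrolled". Protocol 2.2 describes a "pragmatic randomized controlled trial across six hospitals in a healthcare system". Protocol 3.2.1 refers to "those patients who were admitted to the Cancer Center, which was not included as a site" and does not say whether that centre is one of the six. The number of clusters is therefore at most six.

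Assignment was mainly by patient. Tech followed the last four digits of the record number (Protocol 3.2.1), and "Touch randomization occurred at consent using the randomizer function in Qualtrics" (Protocol 3.2.2). The exception is in Protocol 4.2.1: patients who had an activated account or "were in a Full-Tech unit prior to the study start were manually assigned Full-Tech regardless of their MRN".

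SAP 1.1 sets the standard for every result: "For all statistical tests, a p-value of 0.05 was used to assess significance and 95% confidence intervals were reported". H1 to H3 use negative binomial, logistic or fractional logistic models; for example, SAP 1.5.1 specifies "Negative binomial model with non-interacted and interacted study arms as binomial predictors". Only H4 (SAP 1.8.1) uses OLS. SAP 1.3 names the software but no variance or degrees-of-freedom option. The one check on the clustering is a sensitivity analysis of patients transferred between hospitals (SAP 1.4.2 and 1.4.9).

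**The concern.** A cluster-robust variance is built from one score total per cluster. Its precision depends on the number of hospitals, so analysing 2,892 patients does not help. With six totals the estimated standard error is noisy, and dividing by it gives a statistic with much heavier tails than the normal. If one or two hospitals hold most of the patients, the standard error is also biased downward.

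The SAP does not say how this is handled. The same text permits a test near 5% or one at more than twice that, and both primary hypotheses depend on which was used. The transfer analysis asks whether patients were placed in the right hospital, not whether six hospitals are enough.

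**Working it through.** **Inputs from the documents.** Significance level 0.05 with 95% intervals (SAP 1.1); G = 6 hospitals, possibly 5 (Protocol 2.2, 3.2.1); N = 2,892, Full-Tech 74.2%, High-Touch 31.2% (Protocol Table 2).

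**Assumed, because the documents are silent.** A normal reference for the H1 to H3 models, the usual choice for models of this type. Hospital shares: equal, 35-25-15-12-8-5%, or 55-20-10-8-5-2%. Logistic outcome rate 30% with a between-hospital SD of 5 points. Negative binomial log-rate SD 0.2, dispersion 1 treated as known, exposure offset.

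**Plan's own figure.** P(|Z| > 1.960) = 5.0%. This holds only if the standardised estimate is normal.

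**Equal hospitals, analytic.** The variance is H⁻¹(Σ U_g U_g′)H⁻¹ × G/(G−1), where U_g is the score total for hospital g. The Wald statistic is then approximately t with G−1 df:

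- G = 6: P(|t₅| > 1.960) = 10.7%; coverage 100 − 10.7 = 89.3%.
- G = 5: P(|t₄| > 1.960) = 12.2%; coverage 87.8%.
- G = 6 without the G/(G−1) factor: 13.4%.
- G = 6 against the t(5) critical value of 2.571: 5.0%. Intervals are 2.571/1.960 = 1.31 times as wide.

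**Simulation under the null.** Patients were randomised individually. The table is for the Touch coefficient, with 4,000 trials per cell (Monte Carlo SE about 0.5 points) and the G/(G−1) factor included. Sizes are in %.

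| Hospital shares | Normal: logistic | Normal: neg. binomial | t(5): logistic | t(5): neg. binomial | t(5): OLS | Mean SE / true SD |
|---|---|---|---|---|---|---|
| Equal | 11.2 | 11.6 | 5.1 | 5.8 | 4.9 | 0.93–0.95 |
| 35-25-15-12-8-5 | 12.6 | 13.4 | 6.0 | 7.0 | 6.7 | 0.88–0.91 |
| 55-20-10-8-5-2 | 17.1 | 17.9 | 10.0 | 10.2 | 9.1 | 0.81–0.82 |

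A ratio near 0.95 in the last column is expected from the square root of any 5-df variance estimate. Only the fall below that shows bias from unequal sizes. The Tech and interaction coefficients gave 10–18% with a normal reference.

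A second logistic simulation used 60:40 and 1:1 allocation and 20,000 trials per scenario. With a normal reference it gave 10.4–11.1% for equal hospitals, 10.8–11.7% for 25-20-17-15-13-10%, and 12.6–14.9% for 35-25-15-12-8-5%. The upper ends of the wider ranges arise when treatment effects vary by hospital.

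**Candidate remedies.** Sizes are in %, in the order of the three share patterns where three values are given.

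| Method | Common effect | Effects vary by hospital, mean zero |
|---|---|---|
| Hospital indicators + robust SE | 4.7–5.6 | logistic 14.1 / 16.7 / 24.3; neg. binomial 20.0 / 24.4 / 32.1 |
| Hospital clustering, t(5) | see table above | logistic 5.0 / 7.4 / 13.4; neg. binomial 5.4 / 8.8 / 16.4 |
| Score wild bootstrap, six-point weights (2,500 trials) | 4.3–6.5 | 4.5–5.8 |

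The varying effects had SD 4 points (logistic) or log-rate SD 0.12 (negative binomial). A bias-reduced variance with Satterthwaite t was tested only in a linear probability model (3,000 trials). Its size was 2.8–4.8%, with mean df 5.0 / 3.4 / 2.2.

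**The case against.** The strongest reply is that the documents show an unstated reference distribution, not a test running at 11%. If the analysts used t(5), equal hospitals give 5.1% (logistic) and 5.8% (negative binomial), which is close to nominal. This stands as a condition on the size. It does not remove the gap, because the SAP text allows either reference and t(5) still gives about 10% when hospitals are very unequal.

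Second, no hospital sizes are published, so every figure above about 11% (12% with five hospitals) is a scenario. With mild imbalance the size hardly moves. This also stands.

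Third, the simulations do not cover the whole plan. The fractional logistic models, the weighted per-protocol analysis, the Full-Tech sub-sample and the smaller H2 and H3 samples were not reproduced. Changing the allocation share and the sample size made little difference in logistic checks, so this limits the scope and leaves the result in place.

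Fourth, since patients were mostly randomised individually, hospital clustering might seem harmless or unnecessary. It is not harmless: the simulations randomise individually and the test is still too liberal. Whether it is necessary depends on the inference target. Dropping it is safe only if effects do not vary by hospital or inference is confined to these hospitals.

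**Conclusion.** The concern holds. SAP 1.4.2 relies on a large-cluster method with at most six clusters and names nothing to correct it. With a normal reference, the nominal 5% tests of H1 to H3 have size of about 11% at best, and 95% intervals cover about 89%. The assumed unequal splits give 12.6 to 17.9%. H4, if referred to t(5), is near nominal unless hospitals are very unequal.

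The conclusion rests on the assumed normal reference. Beyond 11% it also rests on hospital sizes that the documents do not give. These figures are per test and are separate from the decision not to adjust for multiplicity. This should be fixed; confidence in the exact size is medium.

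**What to change.** In SAP 1.4.2, state the inference target, the number of clusters and the patients per hospital. Replace the uncorrected estimator with one of the following as the main method, and report the other as a sensitivity analysis.

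1. **Effects may vary by hospital and inference goes beyond these hospitals.** Keep hospital clustering with a null-imposed wild cluster bootstrap, in its score version for the logistic and negative binomial models. Use six-point (Webb) weights. Two-point weights on six clusters give 2⁶ = 64 sign patterns in mirror pairs, so p-values move in steps of 1/32 = 0.031; with five clusters the step is 1/16 = 0.0625 and 0.05 cannot be reached. A bias-reduced variance with Satterthwaite t is the alternative, but its performance here was checked only in a linear model.
2. **Inference is to these hospitals only.** Use hospital indicators with heteroskedasticity-robust standard errors. This does not deal with unit-level variation or with the Full-Tech assignments that followed unit, and the SAP should say so.

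**Cost.** One paragraph, plus a re-run of existing data over many outcomes, with and without interaction, in two populations.

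- Option 1 usually widens intervals. The t(5) reference alone adds 31%. In the most unequal case the bias-reduced interval was about 2.2 times as wide as the uncorrected normal one.
- Option 2 adds up to five parameters. It changes the statements such as "No covariates were added to this analysis" in SAP 1.5.1–1.5.3, 1.6.2a, 1.6.2b, 1.7.1–1.7.4 and 1.8.1, and the covariate lines in 1.6.1 and 1.7.5. Its odds ratios become conditional on hospital. The log odds ratio shifts by about 1% if hospital rates vary with SD 5 points around 30%.

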4.2 Adherence and protocol deviations

The HT2 study was designed as a pragmatic study with the interventions conducted using a *per protocol* approach.

Protocol deviations

Protocol deviations may have occurred if:

1. a participant consented to participate in the study but subsequently requested a change in Tech status to the OSUWMC;
2. a participant was admitted to the OSUWMC, was assigned to the Lite intervention, and was subsequently admitted to a unit that always received the Full version of MyChart Bedside.

In these cases, the individual was removed from the study.

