### 1.6.1 Outcome 1 – Patient satisfaction was dependent on treatment

*Outcome specification:* Variations of this outcome were available in each survey. The following 5-point Likert scale survey items were explored as individual items dichotomized to one “most positive” response versus all other responses:

- **15-day Post-discharge survey:** In your most recent hospital experience, how satisfied were you with the interactions you had with your healthcare professionals?
- **15-day Post-discharge survey:** In your most recent hospital experience, how satisfied were you with how well your healthcare professionals responded to your concerns?
- **6-month Post-discharge survey:** In the past six months, how satisfied were you with the interactions you had with your healthcare professionals?
- **6-month Post-discharge survey:** In the past six months, how satisfied were you with how well your healthcare professionals responded to your concerns?

*Statistical Model:* Logistic regression models with and without an interaction of Tech and Touch were reported.

*Covariates:* The corresponding survey item from the Admission Survey was used as a covariate for the items listed above. The two relevant survey items were:

- **Admission survey:** In the past 12 months, how satisfied were you with the interactions you had with your healthcare professional?
- **Admission survey:** In the past 12 months, how satisfied were you with how well your healthcare professionals responded to your concerns?

*Sub-sample analysis:* No sub-sample analyses were considered for this outcome.

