### 1.7.5 Outcome 5 – Frequency of use for Prior MyChart Users

*Outcome specification:* The count of MyChart sessions occurring between the date of enrollment in the study and the cutoff date. This variable was specified as a count variable. New MyChart Users and Never MyChart Users were not included in the analysis for this outcome.

*Statistical model:* Negative binomial regression model for counts of sessions with non-interacted and interacted study arms as binomial predictors (see Equation 4).

Equation 4: If Prior MyChart User =1;  $y = X_{Tech} + X_{Touch} + X_{Tech*Touch}$

*Covariates:* The count of pre-enrollment sessions was included as a covariate in the model to control for previous use.

*Sub-sample analysis:* No sub-sample analyses were considered for this outcome.

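### Hospital enters only the standard errors, so if the non-random routes into Full-Tech differ by enrollment hospital, hospital differences in outcome enter the Tech estimate

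*SAP*

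**What the plan says.** **Model.** SAP 1.4.2 sets a general regression on Tech, Touch and their product, with tablet provision length as an offset. It names "differences in policies and procedures across hospitals and units" among its reasons for cluster-robust standard errors, and continues: "The analysis clusters study participants by the hospital where the study participant was enrolled". Hospital has no other role.

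**Covariates.** For Bedside sessions, SAP 1.5.1 says: "No covariates were added to this analysis". Sections 1.5.2, 1.5.3, 1.6.2a, 1.6.2b, 1.7.1 to 1.7.4 and 1.8.1 likewise have none. There are two exceptions:
- Satisfaction (SAP 1.6.1): "The corresponding survey item from the Admission Survey was used as a covariate for the items listed above".
- Prior MyChart users (SAP 1.7.5): "The count of pre-enrollment sessions was included as a covariate in the model to control for previous use".

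The per-protocol weights (SAP 1.4.1) use five patient characteristics and not hospital. The transfer sensitivity analysis (SAP 1.4.2 and 1.4.9) concerns patients who moved between hospitals.

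**How Tech status arose.** Protocol 3.2.1 assigns Tech patient by patient from the last four MRN digits. Patients with earlier access to the Full version kept it and were not randomized. Under Protocol 4.2.1, amendment 4, individuals who had already activated an account or "were in a Full-Tech unit prior to the study start were manually assigned Full-Tech regardless of their MRN". Under Protocol 4.2, a Lite participant who was "subsequently admitted to a unit that always received the Full version of MyChart Bedside" was removed from the study. Protocol Table 2 reports 2,147 Full and 745 Lite, against a 60:40 allocation.

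**The concern.** The plan treats hospital differences as a matter of variance only. A cluster-robust standard error changes the width of the interval and leaves the coefficient where it was. If Full patients sit disproportionately in hospitals where portal use, adoption or self-efficacy is higher or lower for other reasons, the Tech coefficient carries some of that difference.

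Randomization by MRN would normally answer this, because it balances hospital between arms in expectation. Here the realized split is far from the allocated one, and the documented reasons for Full status include where a patient had been before. Balance by hospital therefore cannot be assumed for the Tech contrast, which is part of both primary hypotheses.

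**Working it through.** **1. Departure from the allocation.** Inputs are from Protocol 3.1.3 and Table 2.
- Full share = 2,147 / 2,892 = 0.742, which reproduces the Protocol's 74.2%.
- Against 0.60: z = (0.7424 − 0.60) / √(0.60 × 0.40 / 2,892) = 15.6. Chance does not explain the gap.

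**2. Share of a hospital difference that enters the Tech estimate.** Assume a group of hospitals, A, holds a fraction *s* of participants and all the excess Full patients, and that the other hospitals are at 0.60. Let *a* be the Full share in A and *D* the outcome difference between A and the rest. For a simple Full-minus-Lite difference on a linear scale:
- a = (0.742 − 0.60(1 − s)) / s
- fraction of D that enters = P(A given Full) − P(A given Lite) = s·a/0.742 − s(1 − a)/0.258

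| s (assumed) | a | Fraction of D |
|---|---|---|
| 0.4 | 0.955 | 0.515 − 0.070 = 0.445 |
| 0.5 | 0.884 | 0.596 − 0.225 = 0.371 |
| 0.6 | 0.837 | 0.677 − 0.380 = 0.297 |
| 1.0 (even spread) | 0.742 | 1 − 1 = 0 |

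The documents give neither *s* nor *D*. As an illustration with assumed values of D, over s = 0.4 to 0.6:
- D = 2 points gives 0.6 to 0.9 points (2 × 0.297 and 2 × 0.445).
- D = 5 points gives 1.5 to 2.2 points.

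For scale, Protocol 3.4 expected to detect changes of 2.2% to 3.8% in patient satisfaction scores.

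**3. Spread of the Tech estimate with and without hospital in the model.** This is a simulation of a linear outcome with no Tech effect, 2,892 participants, six hospitals of assumed unequal size and 4,000 runs. The intra-hospital correlations (ICC) are assumed. Entries are the SD of the estimate without hospital divided by the SD with hospital indicators.

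| Full share by hospital (assumed) | ICC 0.01 | ICC 0.02 | ICC 0.05 |
|---|---|---|---|
| Equal | 1.00 | 1.01 | 1.02 |
| 70% to 95% | 1.03 | 1.07 | 1.18 |
| 60% to 100% | 1.19 | 1.42 | 1.92 |

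With an equal mix there is almost nothing to gain, in line with 1/√(1 − ICC) = 1.005 at 0.01 and 1.026 at 0.05. The benefit appears only when the Full share varies by hospital. Type I error with hospital indicators was 0.045 to 0.057 throughout.

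**4. Patients not randomized to Full.** If the 745 Lite patients are 40% of those randomized, then 745 / 0.40 ≈ 1,863 were randomized. The excess Full is 2,892 − 1,863 ≈ 1,030, or 1,030 / 2,147 = 48% of the Full arm. This is an upper-end reading, because removing Lite patients also raises the Full share. If non-randomized Full patients differ in outcome by an assumed 5 points, the Tech estimate shifts by 5 times their share of the Full arm: 0.5 points at 10%, 1.25 at 25% and 2.4 at 48%. Hospital indicators do not remove this shift, since it comes from earlier exposure.

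**The case against.** The strongest reply is that Tech was randomized by patient, neither randomization is described as stratified by hospital, and so a hospital term is optional. For patients whose status came from their MRN this stands: omitting hospital causes no bias and little loss of precision.

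Several stronger readings are tempting, and the documents do not support them.
- **That whole units were manually made Full.** Amendment 4 concerns individuals with an account or a Full-Tech unit stay before study start. Some units always had Full, but the only such area named, the Cancer Center, was not a study site (Protocol 3.2.1). An always-Full unit to which a Lite patient later moved need not be in the enrollment hospital.
- **That 74.2% Full shows imbalance between hospitals.** Patient-level routes could also produce it, such as removal after a request to change Tech status (Protocol 4.2) or exclusion of those who accessed both versions (Protocol 4.2.1).
- **That leaving hospital out inflates the standard error.** With an equal mix the effect is about 0% to 2.6% on a linear scale. In the logistic models, adding hospital changes the odds ratio being estimated and usually does not shrink its standard error.
- **That every outcome is equally exposed.** The baseline covariates in SAP 1.6.1 and 1.7.5 may absorb part of a stable hospital difference. Analyses within Full-Tech only (SAP 1.4.3 and 1.5.3) contain no Tech contrast.

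It is also fair to say that the documents do not state whether non-randomized Full patients are in the main population, which SAP 1.4.1 defines by randomized group. None of this shows that the Full share is even across hospitals, and the plan reports nothing that would let a reader check.

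**Conclusion.** The point holds as a conditional one. Two facts are certain: hospital is in no mean model or weight, and the realized Tech split does not follow the randomization. Whether this displaces the Tech estimate depends on how the Full share varies by enrollment hospital, which is not reported.

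The share of a between-hospital difference that enters the Tech estimate runs from zero to about 30% to 45%. The upper figures need all the excess Full to lie in hospitals with 40% to 60% of participants, so they mark an extreme case and are not an estimate. The calculation is linear and ignores Touch. The exposure is clearest for the Tech contrasts without covariates (H1, H2b, H3a and H4) and weaker for H2a and H3b. The case for change rests on protecting the point estimate; little gain in precision should be claimed. Prior exposure among non-randomized Full patients is a separate source of bias that hospital adjustment would leave in place.

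**What to change.** All three steps use data that the study should already hold.

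1. **Tabulate** Full:Lite and High:Low by enrollment hospital. Show separately the numbers randomized by MRN, assigned or kept Full outside the randomization, and removed after a move to an always-Full unit. This alone would show whether the Full mix differs enough between hospitals to matter. It also exposes the removals from the Lite arm, which the next two steps do not reverse.
2. **Add enrollment-hospital indicators** to Equations 1 to 4, with one sentence in SAP 1.4.2. The variable already defines the clusters. Six hospitals need five extra parameters. Pool very small hospitals by a stated rule, especially for the survey outcomes and the H3 subsets, whose denominators are smaller than 2,892. The cost is that odds ratios become conditional on hospital, and cells may be sparse in those subsets.
3. **Restrict the main Tech comparison** to patients whose Tech status was set by the MRN randomization, and show the full set as a sensitivity analysis. On the upper-end reading the Full arm falls from 2,147 to about 1,118 (0.60 × 1,863). For an outcome with equal variance in both arms, the standard error of the Tech contrast then rises by the factor √(1/745 + 1/1,118) / √(1/745 + 1/2,147) = 0.0473 / 0.0425 = 1.11, or about 11%. It rises less if fewer patients were assigned outside the randomization.
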